6.2 Risks Related to Clinical Relevance of Test Results

If any lab tests, questionnaires or any other measurements made during the screening or procedures of this protocol show clinically significant abnormalities that may impact the health

and well-being of the subjects, they will be notified by a qualified member of the research team. Appropriate follow-up with their primary care physician will be planned. If needed, the research team will refer subjects to a health care provider.

6.3 Safety and Event Reporting

Adverse events, non-compliance both serious or continuing, protocol deviations both major and minor, as well as unanticipated problems are defined & described by the NIH Office of Human Subjects Research Protection policy #801, and will be reported in accordance with this policy.

6.4 Data and Safety Monitoring Plan

Given the modest level of risk involved in the research, no Data and Safety Monitoring Board will be instituted. Medical oversight will be provided by the Medically Accountable Investigator. Adverse events will be recorded and monitored by the Principal Investigator. The study will be subject to audits to ensure compliance with the protocol and applicable regulatory requirements consistent with the NIDDK Monitoring plan. Audit results will be reported to the Principal Investigator for further reporting as appropriate. Study documents and pertinent hospital or clinical records will be reviewed to verify that the conduct of the study is consistent with the protocol plan.

7. Investigator Responsibilities

The Principal Investigator, [name], assumes responsibility for the study design, supervision of Associate Investigators and staff, and general management of subjects and PII.

Associate Investigators will be involved with distinct aspects of the protocol, and responsibilities have been outlined accordingly. [name], CRNP will oversee prescreening, participant management and admission, physical health assessments, and data acquisition and analysis. [name] will assist in data analysis. [name] will assist with psychophysical testing and taste genotyping. [name] will assist with sensory and palatability assessments.

8. Recruitment Strategies

Adult subjects will be recruited from the community through advertisements in clinicaltrials.gov and possibly, local flyers, newspapers, magazines, internet, mail, radio, or television. Advertisements will be developed with the assistance of the patient recruitment office and will be submitted to the IRB prior to their use.

The age range for inclusion in this protocol is 18-50 years. The rationale for excluding subjects older than 50 years is multi-fold. First, a number of the metabolic outcome variables of this protocol have been shown to change significantly with aging (e.g., metabolic rate and body composition). Second, much of the current information on our primary outcome measurements was gathered from subjects within the age range specified by this protocol; therefore, we believe that this age range is appropriate as it allows us to put our results into direct context with the current knowledge base.

8.1 Recruitment of Women, Children, Minorities and Other Vulnerable Individuals

NIH employees will be eligible to participate in this study. We will use appropriate methods to recruit staff participants, posting flyers where public announcements are permitted (rather than direct solicitation of subordinates). Staff subject's data will be kept private and confidential. We will provide the NIH Information Sheet on Staff Research Participation to staff prior to obtaining consent to help them understand the possible consequences of their participation. Neither participation nor refusal to participate as a research subject will have an effect, either beneficial or adverse, on the staff participant's employment or position at NIH. Additional safeguards may be employed, including independent consent monitoring, training study staff on how to obtain/manage potentially sensitive information about a co-worker.

We will actively encourage the participation of women and minorities. We expect women to represent approximately half of the study population, and we anticipate that African-Americans and Hispanics will constitute at least 20% of enrollees.

We have deliberately chosen not to study children and adolescents at this time. At present, there is no information suggesting that the metabolic responses to alterations of dietary macronutrients are likely different in adults and children and so we see no compelling reason to expose children to the rigors and inconvenience of this type of study. We fully recognize, however, that the insights derived from the data analysis in this study may very well direct our attention to other potentially fruitful areas of clinical research involving child health. We have also chosen not to enroll pregnant women at this time, as there is no known prospect of direct benefit for the woman or the fetus, and we see no reason to expose either the woman or the fetus to the rigors and inconvenience of this type of study.

Individuals who are unable to provide consent will also not be enrolled. This is based on the strenuous demands of the study and the requirement to be able to read, understand and carefully follow study directions, and fill out several questionnaires throughout the study. We have chosen not to enroll non-English speaking participants, as these questionnaires are not currently available in languages other than English. We will make every effort to enroll minority men and women.

9. Subject Withdrawal

The subject may choose not to be in the study, or, if they agree to be in the study, they may withdraw from the study at any time. We will employ a recruit to replace strategy to accrue a total of 20 completers. If a subject withdraws from the study, no new data will be collected for study purposes unless the data concern an adverse event related to the study. If such an adverse event occurs, we may need to review the subjects' entire medical record. Subjects' decision not to participate or to withdraw from the study will not involve any penalty or loss of benefits to which they are entitled and will not affect access to health care at the National Institutes of Health.

Also, there are several conditions that require the Principal/Co-Investigator to drop a study volunteer from this protocol, which include but are not limited to the following:

- Development of any new medical condition or start of medications that would have prevented enrollment in this study as it pertains to the exclusion criteria
- Inability or unwillingness to comply with study requirements
- The subject becomes pregnant during the course of the study
- The Principal/Co-Investigator of the study site deems it unsafe to remain in the study

The study is terminated

10. Research Use, Storage, and Disposition of Human Subjects' Samples and Data

As with all clinical data, the findings will be kept confidential. Volunteer clinical data will be protected and tracked using standard operating procedures in the medical record department. All research charts and records will be kept in a secure place in a locked file cabinet in the office of the Principal Investigator. All research samples and data will be identified by a study code linked to the subject's name and the code and the results of all analyses will be kept strictly confidential. All research samples (e.g., blood) will be coded for storage in refrigerators and freezers in a locked NIH laboratories. These samples will be stored indefinitely and may be used for future research. The IRB will be notified in the event these samples are accidentally destroyed, lost or are anonymized.

Some clinically relevant research data will be stored indefinitely in the medical record and will be accessible to the subject for review by others of the participant's choosing (doctors, insurance companies etc.) after executing a release of information. This and other data will be maintained in databases, password protected and secure.

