While there is much debate surrounding the effect of diet composition on energy intake, most studies rely on self-reported measurements of diet which are known to provide inaccurate estimates of energy and macronutrient intake [10]. Furthermore, outpatient studies cannot ensure that subjects are exposed to only the diets under investigation and cannot adequately assess adherence. Only two previous studies have used objective methods to measure significant effects on ad libitum energy intake over 14-day periods between diets differing in fat (15-60% of total calories from fat) and diets differing in carbohydrate (27-67% of total calories from carbohydrate) [11, 12]. However, proponents of low-carbohydrate and low-fat diets often claim that the benefits of such diets require that the restricted macronutrient be limited to $\leq 15\%$ of total calories. Furthermore, the previous ad libitum feeding studies employed 3-day rotating menus with identical foods in each test diet. Thus, the limited variety of foods raises questions about ecological validity since the types of foods typically consumed on a low-carbohydrate, high-fat (LCHF) diet often differ widely from the foods consumed on a high-carbohydrate, low-fat (HCLF) diet. For example, LCHF diets typically employ a variety of animal products and avoid foods high in sugar and starch. In contrast, LFHC diets are often plant-based with most calories derived from high-starch foods and the use of cooking fats and spreads is restricted.

2. Study Objectives

In this study, we will investigate *ad libitum* food intake of 20 healthy adult volunteers who will each complete a 4-week stay at the NIH. During their stay, they will consume a LCHF diet and a LFHC diet for 2 weeks each, in random order. We will collect information (primary and exploratory endpoints detailed below) about energy intake and metabolic changes, in response to the two test diets. The test diets will be presented to subjects in amounts exceeding their daily energy requirements; subjects will be instructed to eat as much or as little of each diet as desired.

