3.1 Subjects

Adult subjects (18-50 years of age) will be recruited to the study via the NIH Patient Recruitment and Public Liaison Office. Telephone pre-screening will exclude subjects with diabetes or any other metabolic disorders, and those who require assistance to complete activities of daily living. All others will be contacted by the protocol team to review exclusion criteria. To determine eligibility for the MRI component of the study, we will ask subjects about prior hearing loss that may be impacted by the MRI or metal implants such as pacemakers, metallic prostheses such as cochlear implants or heart valves, shrapnel fragments, etc.. All subjects will be fully informed of the nature, risks, and potential benefits of the study prior to giving written consent. However, subjects will not be explicitly told that the primary aims of the study are to measure differences in food intake between the test diets. Rather, they will be informed that the purpose of the study is to examine the health and metabolic effects of a low-carbohydrate, high-fat diet compared to a low-fat, high carbohydrate diet. Because it is not possible to blind subjects to the diets, concealing the primary aims of the study will limit the potential confound that subjects consciously alter their food intake behavior to purposefully increase or decrease their intake of the diet to influence the primary outcomes.

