4.9 Oral glucose tolerance test

After an overnight fast, 75 grams of oral glucose will be administered. Blood samples will be obtained at 0, 10, 20, 30, 60, 90, 120, and 180 minutes to measure glucose, insulin, C-peptide, free fatty acid, and lactate concentrations. Blood samples for research will also be collected. If the results of this test indicate an abnormal blood glucose level consistent with potential diagnosis of diabetes, the subject will be informed by a physician on the research team prior to being discharged from the study. However, such abnormal results may not be revealed until the end of the study to avoid influencing eating behavior and risk compromising the primary aim of the study. Note that the planned experimental manipulation of diet composition can impact glucose tolerance. Therefore, an abnormal glucose tolerance test in the present experimental context need not necessarily indicate that the subject has impaired glucose tolerance in the absence of the experimental dietary manipulations.

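### NIH employees are eligible without restriction, so staff likely to know the concealed primary aim could enrol, and no check is described of whether concealment held

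*Combined protocol and SAP*

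**What the plan says.** Section 3.1 states that "subjects will not be explicitly told that the primary aims of the study are to measure differences in food intake between the test diets"; participants hear instead that the study examines health and metabolic effects. The reason follows: "Because it is not possible to blind subjects to the diets, concealing the primary aims of the study will limit the potential confound", meaning deliberate changes in eating that would influence the primary outcomes.

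Both primary aims (Section 2.1) compare ad libitum intake between diets, and under Section 2 "subjects will be instructed to eat as much or as little of each diet as desired". Section 3.3.2 supplies food at about 200% of estimated requirements, so intake can move in either direction. The hypothesis in Section 2 is directional: higher intake on the LCHF diet.

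Section 4.9 allows abnormal glucose tolerance results to be held back until the end of the study, "to avoid influencing eating behavior and risk compromising the primary aim of the study". The sponsor therefore treats influence on eating behaviour as a real threat during conduct as well.

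On recruitment, Section 8.1 says "NIH employees will be eligible to participate in this study". Its staff provisions are recruitment by flyer, confidentiality, an information sheet before consent and no effect on employment. Optional extras include consent monitoring and "training study staff on how to obtain/manage potentially sensitive information about a co-worker".

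**The concern.** Concealment can only protect the outcome in people who do not already know the aim. Someone who works in the investigators' group, on the inpatient unit or in the nutrition service that prepares the test diets may well know that intake is the endpoint, and which diet is expected to give more. Section 8.1, followed as written, admits such a person.

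The outcome is under the participant's own control and each diet is recognisable, so an aware participant can eat differently on each. The crossover does not remove this. A habit that applies equally to both diets cancels in the within-person difference, but a change tied to one diet stays in it. Randomising the order does not help either, because the change follows the diet and not the period. Both primary aims are exposed, and the plan describes nothing that would show afterwards whether it had happened.

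**Working it through.** **Step 1. Does any entry rule cover prior knowledge of the aim?**

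- Section 3.1, telephone pre-screen: metabolic disorders, need for help with daily activities, and MRI suitability. Not covered.
- Section 3.2, 13 exclusions: disease, medication, pregnancy or lactation, exercise, haematocrit (two items), caffeine, alcohol/tobacco/drugs, psychological conditions, implants, dietary restrictions, consent, language. Not covered.
- Section 3.3.1, entry judgement: likely adherence to procedures. Not covered.
- Section 8.1, staff safeguards: undue influence and privacy. Not covered.
- Section 5: no awareness check and no related sensitivity analysis.

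**Step 2. Reproduce the plan's detectable difference (Section 5).** Inputs: day-to-day SD 500-600 kcal/d, zero within-subject correlation, n = 20, 80% power, Type I error 0.05 (sidedness not stated; two-sided used here).

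- SD of one participant's diet difference = √2 × SD/√days.
- 14 days: 500/√14 = 133.6 and 600/√14 = 160.4; times √2 gives 189.0 and 226.8 kcal/d.
- 7 days: 500/√7 = 189.0 and 600/√7 = 226.8; times √2 gives 267.3 and 320.7 kcal/d.
- A paired t-test (noncentral t) then gives 124.8-149.8 kcal/d over 14 days and 176.5-211.8 kcal/d over the final 7 days.

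These match the plan's 125-150 and 175-210 kcal/d, so those figures are a sound yardstick.

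**Step 3. Scale of a possible bias.** If k of 20 participants are aware and each shifts the between-diet difference by x kcal/d in the same direction, the mean moves by k·x/20. Neither k nor x is in the documents; both are assumptions.

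| k | x = 250 | x = 500 |
|---|---|---|
| 1 | 12.5 | 25 |
| 2 | 25 | 50 |
| 3 | 37.5 | 75 |

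Against the 14-day detectable difference:

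- Low end: 12.5/150 = 8% to 12.5/125 = 10%.
- High end: 75/150 = 50% to 75/125 = 60%.

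Against the final-week detectable difference:

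- Low end: 12.5/210 = 6% to 12.5/175 = 7%.
- High end: 75/210 = 36% to 75/175 = 43%.

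**Step 4. Precision of an analysis without aware participants.** With the plan's rounded 14-day standard errors of 190 and 230 kcal/d, the same t-test gives these detectable differences:

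- n = 20: 125.5-151.9 kcal/d
- n = 18: 133.1-161.2 kcal/d
- n = 16: 142.4-172.4 kcal/d

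Losing two participants costs about 6% (133.1/125.5 = 1.06).

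**The case against.** The strongest reply is that the plan contains no error here. Section 3.1 claims only to limit the confound, and broad eligibility is a legitimate choice. The team screens its own volunteers, and the study needs a four-week inpatient stay, so a team member is unlikely to enrol unnoticed. That lowers the probability, but no rule forbids such enrolment.

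Several stronger readings are tempting and are not supported:

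- **That NIH employees in general know the aim.** No passage says so. The mention of a co-worker sits in a list of optional privacy safeguards and could mean any NIH employee.
- **That public advertising gives the aim away.** Section 8 says volunteers come through a trial registry and other media, but the text of those notices is not in the documents.
- **That concealment is the only protection of eating behaviour.** Section 4.9 gives a second one, by a different route.
- **That the bias would favour the hypothesis.** Knowing a hypothesis is not the same as wishing to confirm it, and the Introduction describes competing camps. Aware participants could also pull in opposite directions.
- **That nothing could be examined afterwards.** Staff receive an information sheet before consent, so staff status is known at enrolment. It does not show who knew the aim.
- **That a large effect has been shown.** A 500 kcal/d shift is twice the 250 kcal/d that Section 5 cites as exceeded in earlier diet studies, and it would have to be sustained across both diet periods.

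Consent pages were removed from the documents, so a safeguard or debriefing text there cannot be ruled out. Eligibility rules belong in Section 3.2, however, and that section is present and silent.

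**Conclusion.** The point holds in a limited form. The plan relies on concealment to protect an unblinded outcome that participants control, yet its eligibility rules admit the few people for whom concealment is least likely to work, and no check is described. The group at issue is the investigators' group, 5SWN unit staff and study nutrition staff.

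The likelihood that any of them enrols is unknown, and so are the size and direction of any effect. Under the assumed shifts, one aware participant matters little to moderately (12.5 to 25 kcal/d). Three acting in the same direction could reach 75 kcal/d, half or more of the 14-day detectable difference. This is a cheap improvement to both primary aims; it does not call the sample size or the primary analysis into question.

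**What to change.** 1. Add to Section 3.2 an exclusion for members of the investigators' group, 5SWN unit staff and study nutrition staff, and qualify the staff sentence in Section 8.1 to match.
2. At discharge, after all intake data are collected and before any debriefing, ask one neutral open question: what did the participant think the study was measuring? Pre-specify in Section 5 a supportive sensitivity analysis of both primary aims that leaves out those who name the comparison of food intake between the diets. Keep the primary analysis as it is.

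The criterion should be naming the comparison, not merely saying that food was measured. Participants keep snack records and complete hunger ratings, so many could guess the latter. An open question of this kind should not be added at screening, where it could draw attention to intake.

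Cost: a few staff volunteers are lost, and one question and one analysis are added. The sensitivity analysis is less precise (about 133-161 kcal/d detectable over 14 days at n = 18). It also selects on an answer given after treatment, which may reflect participants noticing their own intake. It can support or qualify the primary result but not replace it.

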10.1 Collaborations Using Stored Samples

[name] at the National University of Singapore will receive data from sensory and palatability assessments of the diets. [name] at the University of Aberdeen will receive urine samples for metabolomics analyses and fecal samples for DNA extraction to reconstruct food intakes. [name] of Keyto, Inc. will provide breath sensor devices and associated software and hardware to measure breath ketones.

Other collaborations will entail (i) identifying candidate biomarkers that discriminate between a low-carbohydrate, high-fat diet and a low-fat, high carbohydrate diet, (ii) identifying a metabolomic profile of a low-carbohydrate, high-fat diet and a low-fat, high carbohydrate diet, (iii) identifying candidate biomarkers of common UPF items and ingredients, such as dietary emulsifiers and high-fructose corn syrup, and (iv) conducting new lipoprotein analyses on stored plasma samples that were originally collected during the mixed meal tests. In addition, characterizing effects on immune phenotypes will take place, measured at the following levels: i) Transcriptome using PBMC, or preferably, whole blood sampled in PAXgene tubes, ii) PBMC phenotype or phosphorylation responses, using mass cytometry measuring ~40 antigens, and iii) Serum/plasma proteomics using SomaLogic to measure 1300 proteins.

All stored samples and data that will be sent to collaborator/s will be stripped of subjects' personal identifiable information based on NIH guidelines. Any future collaborations requiring transfer of stored biological samples and data will be coded after informing the IRB and obtaining necessary assurances from the outside institution. The protocol will be amended and IRB approval will be sought when such collaborations are established.

11. Informed Consent

Written informed consent will be obtained from the participant prior to any screening visits, study procedures or treatments. The Principal Investigator or other designated qualified protocol investigators will explain the study in language understandable to the subject. Sufficient time and

opportunity will be given for discussion of the research as well as to answer any questions they may have, taking care to minimize or eliminate the perception of coercion or undue influence. The participant and the investigator will sign the current IRB-approved informed consent document. A copy of the consent will be given to the subject for future reference. The signed documents will be sent to the Medical Records Department for placement in the subject's permanent CC medical record. Non-English speaking subjects are excluded from the study, therefore the use of the short form consent will not be required. The consent process will additionally be documented in the electronic medical record (CRIS). Principal Investigator, [name], PhD, and Associate Investigator, [name]., Ph.D., [name], M.B.B.S., [name]., R.D., [name], B.S.N.-R.N. and [name], CRNP will obtain the informed consent.

12. Risk/Benefits to Study Participants

This research study involves minimal risk related to the research-indicated procedures. There will be no other direct benefits from participation in this study aside from the knowledge that they are contributing to advancing our understanding of obesity, and that these insights may lead to new treatment options in the future. Abnormal values will be discussed with the study volunteers and forwarded to their primary care physicians with the subject's permission.

13. Remuneration

Subjects will receive payment for the time and effort connected with the study according to the table below. Completion of the entire study needs to be strongly encouraged since incomplete data collection provides no scientific benefit despite introducing a small amount of risk to the subject. Therefore, we propose the following remuneration schedule:

• Total Reimbursement* for completing both diet treatments according to the table below:

* If early discharge occurs prior to study completion, total reimbursement will be at the rate of \$40.00 per day, to include the day of discharge. This reimbursement rate goes into effect if the study is not completed for any reason, i.e. occurrence of illness, family emergency, or per investigator discretion in the event of noncompliance with study procedures. On a case-by-case basis, adjustments may be made to the study schedule, including repeat testing to accommodate subjects who must leave the study temporarily in the event of an emergency.

The total remuneration for this study, if completed, is in accord with our previous study that included the same number of study days (09-DK-0081; \$6520) and a similar level of inconvenience for the volunteers.

Procedure	P	n	TOTAL
Daily Food Adherence	\$60.00	28	\$1,680.00
Inpatient per Diem	\$40.00	28	\$1,120.00
Body Composition (DXA)	\$50.00	5	\$250.00
Indirect Calorimetry with cart	\$50.00	5	\$250.00
Daily Weight and Accelerometer (per week)	\$50.00	4	\$200.00
Meal test	\$100.00	2	\$200.00

Oral Glucose Tolerance Test (OGTT)	\$100.00	2	\$200.00
Doubly Labeled Water (DLW)	\$50.00	2	\$100.00
Questionnaires	\$100.00	1	\$100.00
24hr Respiratory Chamber	\$100.00	4	\$400.00
MRS for Liver Fat	\$100.00	3	\$300.00
Continuous Glucose Monitoring (per week)	\$100.00	4	\$400.00

TOTAL
REMUNERATION:

\$5,200.00

14. References

- 1. Bray, G.A. and B.M. Popkin, *Dietary fat intake does affect obesity!* Am J Clin Nutr, 1998. **68**(6): p. 1157-73.
- 2. Stubbs, R.J., *Nutrition Society Medal Lecture. Appetite, feeding behaviour and energy balance in human subjects.* Proc Nutr Soc, 1998. **57**(3): p. 341-56.
- 3. Ludwig, D.S. and M.I. Friedman, *Increasing adiposity: consequence or cause of overeating?* JAMA, 2014. **311**(21): p. 2167-8.
- 4. Lustig, R.H., *Childhood obesity: behavioral aberration or biochemical drive? Reinterpreting the First Law of Thermodynamics.* Nat Clin Pract Endocrinol Metab, 2006. **2**(8): p. 447-58.
- 5. Taubes, G., The science of obesity: what do we really know about what makes us fat? An essay by Gary Taubes. BMJ, 2013. **346**: p. f1050.
- 6. Wells, J.C. and M. Siervo, *Obesity and energy balance: is the tail wagging the dog?* Eur J Clin Nutr, 2011. **65**(11): p. 1173-89.
- 7. Astwood, E.B., *The heritage of corpulence*. Endocrinology, 1962. **71**: p. 337-41.
- 8. Pennington, A.W., *Obesity*. Med Times, 1952. **80**(7): p. 389-98.
- 9. Pennington, A.W., A reorientation on obesity. N Engl J Med, 1953. **248**(23): p. 959-64.
- 10. Winkler, J.T., The fundamental flaw in obesity research. Obes Rev, 2005. 6(3): p. 199-202.
- 11. Lissner, L., et al., *Dietary fat and the regulation of energy intake in human subjects.* Am J Clin Nutr, 1987. **46**(6): p. 886-92.
- 12. Stubbs, R.J., et al., Covert manipulation of the ratio of dietary fat to carbohydrate and energy density: effect on food intake and energy balance in free-living men eating ad libitum. Am J Clin Nutr, 1995. **62**(2): p. 330-7.
